9.8 Other Safety Assessments

9.8.1 Neurological Examination

A full neurological examination will be performed at the stipulated times (Visit 1 and Visit 10). An abbreviated examination will be performed at Visit 2, Visit 3, Visit 4, Visit 5, Visit 6, Visit 7, Visit 8, Visit 9, and Visit 11.

The full neurological examination will include the following: ankle jerk, vibratory sensation, pain sensation including hyperalgesia, allodynia, muscle strength (0-to-5 rating; ankle dorsiflexion), and gait/station (observation of regular walking, heel-to-toe [tandem] walking, and Romberg test, each assessed as normal or abnormal). The tests of ankle jerk, vibratory sensation, and pain sensation are detailed in the Procedures manual for the Diagnosis of Diabetic Peripheral Neuropathy and Neurological Examination. The assessment on pain symptom will be recorded as “Pain excepting tingling and pins & needles”, “Tingling or pins & needles” or “Dysesthesia”.

The abbreviated examination will include muscle strength and gait/station based on physical examination and medical interview, each assessed as normal or abnormal. Results will be recorded in the CRF.

9.8.2 Ophthalmologic Examination

The ophthalmologic examination will be performed at Visit 1 (allowed to Visit 2) and Visit 10 (allowed to 4 days after). The examination includes examination of visual acuity and funduscopy examination. For a given subject, visual acuity should be examined under the same conditions (uncorrected or corrected) at both visits, and funduscopy should be performed with the same device. Results of visual acuity will be recorded as values, and results of funduscopy examination will be recorded as [Normal / Abnormal, not clinically significant / Abnormal, clinically significant] in the CRF.

9.8.3 Columbia-Suicide Severity Rating Scale¹⁴

The C-SSRS is a tool designed to systematically assess and track suicidal AEs (behavior and ideation). The C-SSRS assesses lifetime suicidality during an initial baseline evaluation using standardized questions, and then prospectively monitors ideations and

behaviors at subsequent follow-up assessments throughout the trial. The reviewer is an investigator or sub-investigator who has completed training prior to the study using the training DVD. The C-SSRS will be administered by the investigator or sub-investigator at each visit. Answers to all relevant questions will be recorded in the CRF. If the subject is judged to have suicidal behavior and/or suicidal ideation, appropriate measures will be implemented such as referring the subject to a specialist as described in the withdrawal procedures (see Section 4.2.3).

9.8.4 Hospital Anxiety and Depression Scale¹²

At each visit, subjects will provide a self-assessment using the HADS. The HADS consists of 7 items to score depression (4-point scale) and 7 items to score anxiety (4-point scale). The subject will respond to each item on the questionnaire. Based on the results, the investigator will check for the presence or absence of depression and/or anxiety. If the subject is judged to have an AE, appropriate measures will be implemented such as referring the subject to a specialist. Results will be recorded in the CRF.

9.8.5 Pregnancy test

Pregnancy tests (urine tests) will be conducted at the stipulated times (Visit 1 and Visit 10), for women of child-bearing potential only. All female subjects will be considered as women of child-bearing potential unless they have undergone surgical sterilization (with documented bilateral oophorectomy) or are postmenopausal and have experienced no menses within the previous 6 months. The subject is considered to be postmenopausal when 12 consecutive months of absence of menstruation is confirmed with no pathological or physiological factors. Results will be recorded in the CRF.

10. OTHER ASSESSMENTS

No other assessments will be performed.

11. STATISTICAL METHODS

11.1 Objective

The primary objective is to compare the change from baseline to Week 14 (Visit 10) in ADPS for 10 mg BID and 15 mg BID of DS-5565 against placebo. The secondary objectives are shown in section 2.1.2.

11.2 General Statistical Considerations

The statistical package SAS[®] (Version 9.2 or higher) will be used to produce tables, figures, and listings.

The modified intent-to-treat (mITT) analysis set will be used as a primary efficacy analysis set for all efficacy analyses and the per-protocol set (PPS) will be used for sensitivity analysis. All safety analyses and pharmacokinetic analyses will be conducted for the safety analysis set and PK analysis set, respectively.

The primary imputation will be based on “nonfuture dependence” model using the pattern mixture approach under the missing not at random (MNAR) mechanism for the missing weekly ADPS data¹⁹⁻²¹. Reason for dropout together with the time of dropout will be used for constructing the missing data pattern. Detail will be at Section 11.5.1 and in the SAP.

Raw data will be presented to the exact precision at which they were collected.

For summary statistics, means and medians will be displayed to one more decimal place than was determined for raw data, dispersion statistics will have two more decimal places, and the minimum and maximum will be displayed to the same number of decimal places as the raw data.

Quantitative data will be tabulated with descriptive summary statistics: arithmetic mean, standard deviation (SD), median, minimum and maximum values, and number of observations. For categorical data, frequency tables will be provided.

All hypothesis testing will provide the *P* values and their corresponding two-sided 95% confidence intervals if applicable. The significance level is 0.05 (two-sided) for all hypothesis testing. The type I error rate will be controlled at less than 0.05 for the multiple comparisons of the primary endpoint of ADPS at Week 14 between each DS-5565 arm (15 mg QD, 10 mg BID, or 15 mg BID) and placebo, using combination approach of Bonferroni-Holm method and gate-keeping procedure (see Section 11.5.1). No adjustment for multiple comparisons will be made for the secondary efficacy analyses.

Analysis for the change from baseline, including the shift table, will be conducted for the

subjects who have an available baseline value and at least one post-randomization value. Subgroup analyses by country (eg, Japan, Korea, and Taiwan) will be conducted for some of efficacy and safety analyses specified in the SAP.

PK analysis will be detailed in the PK analysis plan (PAP).

A detailed SAP and PAP describing the methodology to be used in the final analysis will be prepared before data unblinding. A change in the planned statistical analysis will require a protocol amendment only if it substantively alters the principal features of the protocol. Any deviations from the planned statistical analyses in the protocol will be fully described in the SAP and PAP.

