7. EFFICACY ASSESSMENTS

7.1 Primary Efficacy Variable(s)

Pain score⁷

Each subject will record a pain score in the electronic patient diary once daily from the day after Visit 1 through Visit 10. Every morning upon awakening, prior to taking study medication, the subject will select the number that best describes his or her pain over the past 24 hours on a scale of 0 (no pain) to 10 (worst possible pain). ADPS is the weekly average pain score based on the pain scores from the electronic patient daily pain diaries.

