11.3 Analysis Sets

The randomized analysis set will include all subjects who signed the ICF and were randomized into the study.

The safety analysis set will include all subjects who signed the ICF and received at least one dose of study medication.

The mITT analysis set will include all subjects in the randomized analysis set who received at least one dose of study medication. The mITT analysis set will be used for primary and secondary efficacy analyses.

The PPS will include all subjects in the randomized analysis set who received at least one dose of study medication, and who were sufficiently compliant with the protocol, according to pre-specified criteria that will be finalized prior to database lock. The PPS will be used for sensitivity analyses.

The PK analysis set will include all subjects who signed the ICF and received a dose of DS-5565 and had at least one PK sample collected.

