11.5 Efficacy Analyses

11.5.1 Primary Efficacy Analyses

The primary efficacy analysis will be performed using the mITT analysis set.

Observed ADPS and change from baseline will be summarized by treatment and week (including Week 14/LOCF and Week 14/baseline observation carried forward [BOCF]).

Mean change from baseline in ADPS will be compared between each DS-5565 arm and placebo at Week 14 using the following multiple imputation (MI) method and mixed-effect model for repeated measurements (MMRM)^{17,18} according to the pre-specified test procedure described later in this section.

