The primary imputation will be based on “nonfuture dependence” model¹⁹⁻²¹ using the pattern mixture approach with shifting parameters under the MNAR mechanism for the missing weekly ADPS data. Reason for dropout together with the time of dropout will be used for constructing the missing data pattern. The statistical model used for the MI data generation will be the Markov Chain Monte Carlo (MCMC) method with adjustment for covariates (eg, treatment group, age, sex) to produce a monotone pattern first, and then the imputation will continue using the Regression with Predictive Mean Matching (REGPMM) method for the monotone pattern with the same set of covariates. The imputed value will be set as 10 (the maximal ADPS score) when the imputed value of ADPS score is over 10. Additionally, for dropouts due to LOE, the imputed values will be bound so that a subject’s imputed weekly ADPS after discontinuation cannot be better than that subject’s baseline ADPS. Each complete imputed dataset will be analyzed using the MMRM with treatment, week, treatment-by-week as the fixed effects, week as the repeated measure, and baseline ADPS as the covariate. The results of MMRM analysis from each complete imputed dataset will be combined using Rubin’s rule. All reasons for discontinuation will be categorized, to the extent possible, into either LOE or AE based on detail specified in the Case Report Form. Only reasons that cannot be classified into the above two categories will be considered as “all other reasons (AOR)”. The primary shifting parameter values corresponding to the three categories in the pattern mixture model (PMM) will be chosen as (1.0, 1.0, 0.5) for dropouts due to AE, LOE and AOR, respectively, and the corresponding shifting amount of the weekly ADPS imputed at first missing week is given by $(1.0, 1.0, 0.5) * RSD * U(0,1)$ where $U(0,1)$ is a random variable from a uniform distribution with a range of 0 to 1, and RSD is the residual standard deviation at first missing week after imputation.

The type I error rate will be controlled at less than 0.05 for the multiple comparisons of the primary efficacy analyses in the following multiple test procedure.

- 1) DS-5565 10 mg BID and 15 mg BID will be tested against placebo using Bonferroni-Holm method at significance level of 0.05.
- 2) The following statistical test will be performed according to the result of 1).
 - If both of arms are statistically significant, DS-5565 15 mg QD arm will be

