tested at level of 0.05.

- If neither of the arms is statistically significant, DS-5565 15 mg QD arm will not be tested.
- If either DS-5565 10 mg BID or DS-5565 15 mg BID is statistically significant, DS-5565 15 mg QD arm will be tested at level of 0.025.

Sensitivity analyses will include following:

- The above primary “nonfuture dependence” MNAR model with different shift parameters including (0, 0, 0)
- Placebo multiple imputation^{17,18}
- MMRM using observed data only
- ANCOVA using BOCF
- ANCOVA using LOCF
- The above primary “nonfuture dependence” MNAR model with the same shift parameters as the primary analysis (i.e., (1.0, 1.0, 0.5) using PPS).

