11.2 General Statistical Considerations

The statistical package SAS[®] (Version 9.2 or higher) will be used to produce tables, figures, and listings. All safety and efficacy endpoints will be summarized for the safety analysis set.

No imputation will be done for the missing data of safety valuables. For the efficacy endpoint of SF-MPQ, a missing data will be handled using the standard scoring instructions. Details will be specified in the SAP.

Raw data will be presented to the exact precision at which they were collected.

For summary statistics, means and medians will be displayed to one more decimal place than was determined for raw data dispersion statistics will have two more decimal places, and the minimum and maximum will be displayed to the same number of decimal places as the raw data.

Quantitative data will be tabulated with descriptive summary statistics: arithmetic mean, standard deviation (SD), median, minimum and maximum values, and number of observations. For categorical data, frequency table will be provided.

Analysis for the change from baseline, including the shift table, will be conducted for the subjects who have an available baseline value and at least one post-enrollment (Visit 10) value.

Subgroup analyses by country (eg, Japan, Korea, and Taiwan) will be conducted for some of the efficacy and safety analyses.

A detailed SAP describing the methodology to be used in the final analysis will be prepared before the database lock. A change in the planned statistical analysis will require a protocol amendment only if it substantively alters the principal features of the protocol. Any deviations from the planned statistical analyses in the protocol will be fully described in the SAP.

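### Does the Section 11.2 rule on change-from-baseline analyses remove mITT subjects from the primary analysis?

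*Combined protocol and SAP*

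**What the plan says.** Section 11.2 of the double-blind protocol contains a general rule for change-from-baseline analyses, with shift tables named among them. It restricts them to "subjects who have an available baseline value and at least one post-randomization value". It makes no exception for the primary endpoint, which Section 3.1.3.1 defines as the change in ADPS from baseline to Week 14.

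The same section names mITT as the set for all efficacy analyses. Section 11.3 defines the set without reference to follow-up data: "The mITT analysis set will include all subjects in the randomized analysis set who received at least one dose of study medication". Section 11.5.1 then states: "The primary efficacy analysis will be performed using the mITT analysis set". It imputes missing weekly ADPS, applies a shift at the first missing week, and continues: "Each complete imputed dataset will be analyzed using the MMRM with treatment, week, treatment-by-week as the fixed effects". Its sensitivity analyses include "ANCOVA using BOCF".

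Section 7.1 sets the data collection: "Each subject will record a pain score in the electronic patient diary once daily from the day after Visit 1 through Visit 10".

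The open-label extension protocol, whose efficacy analysis is descriptive only, has a nearly identical sentence in its own Section 11.2, limited to "subjects who have an available baseline value and at least one post-enrollment (Visit 10) value".

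**The concern.** Take a subject who is randomized, takes one dose and never contributes an ADPS afterwards. Sections 11.3 and 11.5.1 put that subject in the primary analysis; the 11.2 sentence, applied to observed data, takes the subject out. No text ranks the two rules. The pointer in 11.2 to Section 11.5.1 and the SAP concerns imputation detail, not who is included.

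If the filter were applied, subjects would be dropped after randomization for a reason that may relate to treatment, such as early intolerance. BOCF would be the most exposed, because its purpose is to count such subjects as having no improvement. The placebo-based imputation and the primary pattern-mixture analysis would also lose subjects whom they are built to handle.

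**Working it through.** **Reading the sections together**

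1. The baseline half of the rule hardly matters. Inclusion criterion 6 requires at least four diary days before randomization.
2. The post-randomization half asks for a value and does not say an observed one. Section 11.5.1 sets no minimum number of observed weeks before imputation. A dosed subject with no later ADPS is first missing at Week 1 and receives imputed values. In each completed dataset that subject has post-randomization values and meets the 11.2 rule.
3. Under BOCF the carried baseline supplies the Week 14 value, with zero change.
4. The 11.2 rule therefore bites only where observed data alone are used: summaries of observed change, shift tables and the observed-data MMRM. There it states what would happen anyway.

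**Who could be affected.** Section 5.1.2 starts treatment at bedtime on Day 1, and Section 7.1 asks for a diary score each morning. The first entry after dosing is due the next morning, so a dosed subject must miss essentially the whole diary to have no value.

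**Size if the filter were applied to observed data**

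Inputs from Section 11.11: 300 placebo and 150 per active arm, SD 1.8, difference 0.6. From the Asian Phase 2 results in Section 1.1.1.5.2: mean placebo improvement 1.5. Assumed: share without post-randomization ADPS xA = 1 to 3% on active and xP = 0.5 to 1% on placebo. Over 450 active and 300 placebo subjects that is 4.5 + 1.5 = 6 to 13.5 + 3 = 16.5 people.

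Standard error of a difference: 1.8 × √(1/300 + 1/150) = 1.8 × 0.1 = 0.18.

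The first row of Table 11-1 gives power of 87.0% (15 mg QD), 89.5% (10 mg BID) and 89.3% (15 mg BID). Simulating the described procedure with 400,000 repetitions gives 87.7%, 90.3% and 90.3%, close enough to use these inputs.

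*BOCF.* With mean improvements mA and mP among subjects with data, excluding the no-data subjects gives mA − mP. Keeping them at zero change gives (1 − xA)mA − (1 − xP)mP. The gap is xA·mA − xP·mP. Put mP = 1.5 and mA = 1.5 + 0.6 = 2.1:

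| xA / xP | Shift in BOCF difference | In standard errors |
|---|---|---|
| 1% / 1% | 0.021 − 0.015 = 0.006 | 0.03 |
| 1% / 0.5% | 0.021 − 0.0075 = 0.0135 | 0.08 |
| 3% / 1% | 0.063 − 0.015 = 0.048 | 0.27 |
| 3% / 0.5% | 0.063 − 0.0075 = 0.0555 | 0.31 |
| 0.5% / 1% (outside the range, reversed) | 0.0105 − 0.015 = −0.0045 | −0.03 |

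The sign turns when xP/xA exceeds 2.1/1.5 = 1.4. The 1.5 is a Week 7 LOCF mean; a BOCF mean, with all dropouts at zero, would probably be smaller, so these shifts probably err high.

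*Primary analysis.* Treatment group is an imputation covariate, so a no-data subject is drawn around the arm's own level and then shifted. For an adverse-event dropout the mean shift is 1.0 × RSD × 0.5. The estimate moves by (xA − xP) × 0.5 × RSD × c, where c is the part of the shift that persists to Week 14. Assume RSD 1.0 to 1.8 and c 0.5 to 1.0:

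- Equal shares: 0.
- 3% / 1%, RSD 1.8, c 0.5: 0.02 × 0.5 × 1.8 × 0.5 = 0.009.
- 3% / 0.5%, RSD 1.8, c 1.0: 0.025 × 0.5 × 1.8 = 0.0225, or 12.5% of the standard error.

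*Placebo-based imputation.* xA × 0.6 = 0.006 to 0.018.

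*Power for a BID arm.* The table compares two rules for a share f of every arm: excluding those subjects, or keeping them with no treatment difference.

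| f | Excluded | Kept | Gap (points) |
|---|---|---|---|
| 1% | 89.9% | 89.6% | 0.3 |
| 3% | 89.3% | 88.2% | 1.1 |
| 5% | 88.4% | 86.7% | 1.7 |

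**The case for a change.** The strongest case for a change is that the template explanation is an inference. The words about the shift table extend the rule and do not confine it. The sentence also comes soon after the paragraph on hypothesis testing. A programmer could select mITT, apply the 11.2 filter and contradict no explicit instruction. Section 7.1 gives no minimum number of diary days for a post-baseline weekly score, so the size of the group is not fixed by the text. A sentence or two would settle it.

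Much of this stands as a comment on drafting: the precedence is unwritten, and the treatment of a no-data subject under LOCF is not spelled out. It does not show that the primary analysis is misdefined. Applying the filter before imputation means setting aside the text written for that analysis in favour of a general sentence. Section 11.2 also leaves the detail to a SAP to be prepared before unblinding, where programming conventions of this kind belong.

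One further point is fair. The primary range above is for dropouts due to adverse events. Section 11.5.1 holds imputed values after dropout for lack of efficacy at no better than baseline. For no-data subjects coded that way, the primary estimate would move at least as much as BOCF. That would require leaving before the first morning entry, or a diary left blank throughout even though sites review it at each visit, and then a judgement of inefficacy. It is possible, but unlikely to describe more than a stray subject.

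**Conclusion.** This is a gap that analysts fill sensibly, and closing it brings no material gain. The specific sections already give the intended answer: mITT subjects without any post-randomization ADPS enter the imputation as first missing at Week 1 and enter BOCF as zero change. The general rule governs observed-change summaries, shift tables and the observed-data MMRM.

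Even on the adverse reading the effect is small. The shift is 0 to about 0.02 point for the primary estimate when the dropouts are due to adverse events, and about 0.006 to 0.056 point for BOCF, against a standard error of 0.18. These figures rest on assumed shares of 1 to 3% active and 0.5 to 1% placebo. The documents give neither the number of such subjects nor their balance across arms, so no direction of bias can be claimed. A sponsor revising Section 11.2 for other reasons could tidy the sentence, but the validity of the primary analysis does not depend on it.

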11.3 Analysis Sets

The randomized analysis set will include all subjects who signed the ICF and were randomized into the study.

The safety analysis set will include all subjects who signed the ICF and received at least one dose of study medication.

The mITT analysis set will include all subjects in the randomized analysis set who received at least one dose of study medication. The mITT analysis set will be used for primary and secondary efficacy analyses.

The PPS will include all subjects in the randomized analysis set who received at least one dose of study medication, and who were sufficiently compliant with the protocol, according to pre-specified criteria that will be finalized prior to database lock. The PPS will be used for sensitivity analyses.

The PK analysis set will include all subjects who signed the ICF and received a dose of DS-5565 and had at least one PK sample collected.

11.4 Study Population Data

Demographic and baseline characteristics will be summarized for the randomized, safety, mITT, PPS, and PK analysis sets.

11.5 Efficacy Analyses

11.5.1 Primary Efficacy Analyses

The primary efficacy analysis will be performed using the mITT analysis set.

Observed ADPS and change from baseline will be summarized by treatment and week (including Week 14/LOCF and Week 14/baseline observation carried forward [BOCF]).

Mean change from baseline in ADPS will be compared between each DS-5565 arm and placebo at Week 14 using the following multiple imputation (MI) method and mixed-effect model for repeated measurements (MMRM)^{17,18} according to the pre-specified test procedure described later in this section.

The primary imputation will be based on “nonfuture dependence” model¹⁹⁻²¹ using the pattern mixture approach with shifting parameters under the MNAR mechanism for the missing weekly ADPS data. Reason for dropout together with the time of dropout will be used for constructing the missing data pattern. The statistical model used for the MI data generation will be the Markov Chain Monte Carlo (MCMC) method with adjustment for covariates (eg, treatment group, age, sex) to produce a monotone pattern first, and then the imputation will continue using the Regression with Predictive Mean Matching (REGPMM) method for the monotone pattern with the same set of covariates. The imputed value will be set as 10 (the maximal ADPS score) when the imputed value of ADPS score is over 10. Additionally, for dropouts due to LOE, the imputed values will be bound so that a subject’s imputed weekly ADPS after discontinuation cannot be better than that subject’s baseline ADPS. Each complete imputed dataset will be analyzed using the MMRM with treatment, week, treatment-by-week as the fixed effects, week as the repeated measure, and baseline ADPS as the covariate. The results of MMRM analysis from each complete imputed dataset will be combined using Rubin’s rule. All reasons for discontinuation will be categorized, to the extent possible, into either LOE or AE based on detail specified in the Case Report Form. Only reasons that cannot be classified into the above two categories will be considered as “all other reasons (AOR)”. The primary shifting parameter values corresponding to the three categories in the pattern mixture model (PMM) will be chosen as (1.0, 1.0, 0.5) for dropouts due to AE, LOE and AOR, respectively, and the corresponding shifting amount of the weekly ADPS imputed at first missing week is given by $(1.0, 1.0, 0.5) * RSD * U(0,1)$ where $U(0,1)$ is a random variable from a uniform distribution with a range of 0 to 1, and RSD is the residual standard deviation at first missing week after imputation.

The type I error rate will be controlled at less than 0.05 for the multiple comparisons of the primary efficacy analyses in the following multiple test procedure.

- 1) DS-5565 10 mg BID and 15 mg BID will be tested against placebo using Bonferroni-Holm method at significance level of 0.05.
- 2) The following statistical test will be performed according to the result of 1).
 - If both of arms are statistically significant, DS-5565 15 mg QD arm will be

tested at level of 0.05.

- If neither of the arms is statistically significant, DS-5565 15 mg QD arm will not be tested.
- If either DS-5565 10 mg BID or DS-5565 15 mg BID is statistically significant, DS-5565 15 mg QD arm will be tested at level of 0.025.

Sensitivity analyses will include following:

- The above primary “nonfuture dependence” MNAR model with different shift parameters including (0, 0, 0)
- Placebo multiple imputation^{17,18}
- MMRM using observed data only
- ANCOVA using BOCF
- ANCOVA using LOCF
- The above primary “nonfuture dependence” MNAR model with the same shift parameters as the primary analysis (i.e., (1.0, 1.0, 0.5) using PPS).

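### The 15 mg QD gatekeeping rule in Section 11.5.1 spends 0.025 twice, so familywise error can reach 7.2% against the stated limit of 5%

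*Combined protocol and SAP*

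**What the plan says.** Section 11.5.1 sets out two steps. In step 1, "DS-5565 10 mg BID and 15 mg BID will be tested against placebo using Bonferroni-Holm method at significance level of 0.05". Step 2 depends on the outcome of step 1 and has three branches for 15 mg QD:

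- Both BID doses significant ("If both of arms are statistically significant, DS-5565 15 mg QD arm will be" tested): level 0.05.
- Neither significant: no test.
- One of the two significant: that dose "is statistically significant, DS-5565 15 mg QD arm will be tested at level of 0.025".

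The error claim appears in the same section: "The type I error rate will be controlled at less than 0.05 for the multiple comparisons of the primary efficacy analyses". Section 11.2 defines the family as the comparisons of "ADPS at Week 14 between each DS-5565 arm (15 mg QD, 10 mg BID, or 15 mg BID) and placebo", so 15 mg QD is inside it although Section 2.1.2 lists it as a secondary objective. Section 11.2 also fixes the sidedness: "The significance level is 0.05 (two-sided) for all hypothesis testing".

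Nothing in the supplied text makes the second BID dose wait for 15 mg QD, or truncates Holm.

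**The concern.** Under Holm, once the smaller BID p-value passes 0.025, the other BID dose is tested at 0.05. If it fails there, the whole 0.05 has been used on that hypothesis. Passing 0.025 to 15 mg QD in exactly this case uses the winning dose's share twice: once to raise the second BID dose from 0.025 to 0.05, and once to open 15 mg QD.

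The situation is plausible. The study hypothesis (Section 2.2) asks only that at least one BID dose be superior. No dose reached significance in the Asian Phase 2 study (Section 1.1.1.5.2), and that study did not include 15 mg QD (Section 3.2.1). If one BID dose wins, the set of further dose claims, on the other BID dose and on 15 mg QD, does not have the joint protection that Section 11.2 states.

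**Working it through.** **Inputs.** Arms of 300 (placebo), 150, 150 and 150, SD 1.8, differences of 0.6 for all doses or 0.4 for QD (Section 11.11); ANOVA-based tests (Section 11.11), hence 750 − 4 = 746 degrees of freedom; two-sided levels (Section 11.2); testing rule (Section 11.5.1). Two comparisons that share the placebo arm have correlation 150/(150 + 300) = 1/3.

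**Step 1: single-comparison power.** Standard error = 1.8 × √(1/150 + 1/300) = 0.18, so 0.6/0.18 = 3.33. Power is 91.5% at level 0.05 and 86.3% at 0.025. The stated BID power of about 89% lies between these, as a step-up in level should give.

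**Step 2: reproduce Table 11-1.** The full procedure was simulated (2,000,000 trials per scenario) under two rules:

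- *Written rule:* complete Holm on the BID doses, then 15 mg QD at 0.05 or 0.025.
- *Loop-back rule:* each BID dose at 0.025; 15 mg QD at 0.025 if one wins or 0.05 if both win; the remaining BID dose retested at 0.05 only if 15 mg QD is rejected.

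| Differences (QD, 10 BID, 15 BID) | Table 11-1 | Written rule | Loop-back rule |
|---|---|---|---|
| 0.6, 0.6, 0.6 | 87.0 / 89.5 / 89.3 | 87.6 / 90.2 / 90.2 | 87.0 / 89.4 / 89.4 |
| 0.4, 0.6, 0.6 | 56.9 / 87.7 / 87.5 | 57.9 / 90.2 / 90.2 | 56.9 / 87.6 / 87.5 |

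(Power in %, in the order QD / 10 mg BID / 15 mg BID.)

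Under the written rule both BID tests finish before 15 mg QD is opened, so BID power cannot depend on the QD effect. In Table 11-1 it falls from 89.5% to 87.7% and from 89.3% to 87.5% when only the QD difference changes. The loop-back rule reproduces all six cells to about 0.1 point; the written rule misses the second-row BID cells by more than 2.5 points.

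**Step 3: familywise error of the written rule.** Let one BID dose be so effective that it is always rejected, with the other BID dose and 15 mg QD null. A false rejection occurs if the null BID dose has p < 0.05 (|Z| > 1.960) or, failing that, 15 mg QD has p < 0.025 (|Z| > 2.241):

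FWER = 1 − P(|Z₁| ≤ 1.960, |Z₂| ≤ 2.241) with correlation 1/3 = 1 − 0.9281 = **0.0719**.

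Of this, 0.0500 comes from the BID dose and 0.0219 is added by 15 mg QD. For comparison, independence gives 1 − 0.95 × 0.975 = 0.0738, and the simple sum is 0.075.

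**Step 4: other configurations (simulated, two-sided FWER in %).**

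| True state | Written rule | Loop-back rule |
|---|---|---|
| No dose works | 4.8 | 4.8 |
| One BID dose at 0.6, others null | 6.3 | 4.3–4.4 |
| One BID dose at 0.8, others null | 7.0–7.1 | 4.7–4.8 |
| One BID dose very effective, others null | 7.2 | 4.8 |
| Both BID doses at 0.6, QD null | 4.2 | 4.0 |
| Both BID doses very effective, QD null | 5.0 | 5.0 |

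Ranges show the spread between separate simulation runs. Counting only false claims in favour of DS-5565, the worst case is 3.6% against the nominal 2.5%.

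**The case against.** Five points can be made for the plan.

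- *Each claim taken alone is within 5%.* In the worst case the null BID dose is falsely rejected 5.0% of the time and 15 mg QD 2.7%; only the union exceeds 5%. This is correct. The Holm test of the BID pair controls error for those two doses, so the primary hypothesis is unaffected. But Section 11.2 claims control over all three comparisons, and that claim concerns the union.
- *15 mg QD is secondary.* It is, but Section 11.2 puts it in the controlled family and Section 11.5.1 gives it alpha under the same guarantee.
- *7.2% is a limiting case.* It needs a large effect of one BID dose and none of the other two doses. The rate is 4.8% if nothing works. Strong control has to hold in every configuration, however, and the planned 0.6 effect already gives 6.3%.
- *The intended procedure may be sound.* Table 11-1 suggests that the simulation used a valid rule. That makes the fault one of description, but the described rule is the one that would be applied.
- *A later SAP may restate the rule.* Section 11.2 foresees a detailed SAP before unblinding. No such text is in the supplied documents, and Section 11.2 refers to Section 11.5.1 for this procedure. The finding applies to the protocol text.

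**Conclusion.** The concern holds. As written, the procedure does not control the familywise error below 0.05 over the three dose comparisons. The maximum is 7.2% two-sided, with 6.3% when one BID dose has the planned effect and the other two doses have none. These figures assume the planned 300:150:150:150 allocation and normally distributed test statistics with a shared placebo arm. The 6.3% also uses the planned SD of 1.8. Missing data do not enter the argument, which concerns the levels alone. The text of Section 11.5.1 and the power in Table 11-1 also rest on different procedures. This must be corrected before unblinding.

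**What to change.** Replace the rule in Section 11.5.1, and carry it into the SAP, with one of the following.

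1. **Loop-back rule (preferred, because it matches Table 11-1).** Test 10 mg BID and 15 mg BID each at 0.025. Test 15 mg QD at 0.05 if both are significant, at 0.025 if exactly one is, and not at all if neither is. Retest the remaining BID dose at 0.05 only if 15 mg QD has been rejected. This is a weighted-Bonferroni graphical procedure, so control at 0.05 holds in every configuration.
2. **Holm, then serial gatekeeping.** Keep Holm on the two BID doses and test 15 mg QD at 0.05 only if both are significant. The worst-case error is 5.0%.

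Both are changes of wording and need no extra subjects. The costs are relative to the power the written rule would have:

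- *Option 1:* BID power goes from 90.2% to 89.4% with differences (0.6, 0.6, 0.6), from 90.2% to about 87.6% with (0.4, 0.6, 0.6), and to about 86.2% if 15 mg QD has no effect. The first two are what Table 11-1 already states. QD power goes from 87.6% to 87.0% and from 57.9% to 56.9%. The second primary dose then depends partly on a secondary dose, which the sponsor should accept knowingly.
- *Option 2:* BID power is unchanged. QD power falls from 87.6% to about 79% in the first scenario and from 57.9% to 54.4% in the second, and Table 11-1 would need to be recomputed.
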